5.3 Exclusion Criteria

1. Females who are pregnant or lactating or planning to become pregnant during the study period.
2. Treatment with the following products:
 - a. Topical acne treatments (other retinoids, antibiotics, benzoyl peroxide, azelaic acid, resorcinol, salicylates, α -hydroxy/glycolic acid), or other topical facial medication (antifungals, steroids, anti-inflammatories) on the treatment area in the 14 days prior to Baseline (Day 1), including prescription and non-prescription products.
 - b. Systemic corticosteroids, systemic acne treatments including systemic antibiotics used for treatment of acne, photosensitizing agents (thiazides, phenothiazines), spironolactone, flutamide, or immunosuppressant drugs in the 30 days prior to Baseline (Day 1).
 - c. Systemic retinoid use (including high-dose vitamin A > 10,000 units per day) in the 180 days prior to Baseline (Day 1).
 - d. Undertaken certain facial procedures such as chemical peel, laser treatment, photodynamic therapy, acne surgery, cryodestruction or chemodestruction, x-ray therapy, intralesional steroids, dermabrasion, or depilation (except eyebrow shaping) in the 30 days prior to Baseline (Day 1). After the subject is enrolled in the study, eyebrow shaping (except for tweezing) is prohibited.
 - e. Treatment with a medication or procedure that, in the opinion of the investigator, would put the subject at unacceptable risk for participation in the study or may interfere with evaluations in the study.
 - f. Treatment with an investigational product or device in the 30 days prior to Baseline (Day 1).
3. Known allergic reaction to retinoids or tazarotene or any of the other ingredients of these products. The inactive ingredients are sodium lauryl sulphate, stearyl alcohol, cetyl alcohol, gluconolactone, Vitamin E polyethylene glycol succinate, glycerin, carbomer P 971, propylparaben, methylparaben, edetate disodium, butylated hydroxytoluene, medium-chain triglyceride, trolamine, and purified water.
4. Presence of any facial skin disease or condition that would interfere with the study or place the subject at unacceptable risk including sunburn, rosacea, seborrheic dermatitis, perioral dermatitis, lupus, dermatomyositis, psoriasis, eczema, squamous cell carcinoma, acneiform eruptions caused by medications, steroid acne, steroid folliculitis, bacterial folliculitis, or any other facial disease or condition.

5. Excessive facial hair (i.e., heavy beard or mustache), facial tattoos, or facial disfigurement, excessive hair on the neck, upper chest, shoulders and upper back region that would interfere with study assessments.
6. Subjects with a serious and/or chronic medical condition such as chronic or active liver disease, renal impairment, heart disease, severe respiratory disease, rheumatoid arthritis, current malignancies, immunocompromised conditions, or any other disease that, in the opinion of the investigator, would interfere with the study or place the subject at unacceptable risk.
7. Subjects who have been treated for alcohol dependence or alcohol or drug abuse in the year prior to Baseline (Day 1).
8. Subjects who have been in another investigational trial within 30 days of Baseline (Day 1).
9. Subjects may not have a personal relationship with any member of the study staff or be part of the staff at the medical practice.
10. HIV Ag/Ab Combo, Hepatitis B (HBsAg (B)) and Hepatitis C (anti-HCV (C)) positive subjects.

Subjects must not use the medications or procedures shown in [Table 4](#) for the period specified before Baseline (Day 1). Table 4 also indicates whether the medications or procedures are allowed or prohibited during the study (after Day 1).

Table 4: Restriction Periods (Prior to Day -1)

Product	Washout Period	During Study
Topical acne treatments (retinoids, antibiotics, benzoyl peroxide, azelaic acid, resorcinol, salicylates, α-hydroxy/glycolic acid), or other topical facial medication (antifungals, steroids, anti-inflammatories) on the treatment area, including prescription and non-prescription products	14 days	Prohibited
Systemic corticosteroids, systemic acne treatments including systemic antibiotics used for acne treatment, photosensitizing agents (thiazides, phenothiazines), spironolactone, flutamide, or immunosuppressant drugs	30 days	Prohibited
Other investigational product or device		
Systemic antibacterials	Allowed except systemic antibiotics used for acne treatment, which will require a 30-day washout period	Up to 10 days allowed for indications other than acne
Facial procedures such as chemical peel, laser treatment, photodynamic therapy, acne surgery, cryodestruction or chemodestruction, x-ray therapy, intralesional steroids, dermabrasion, or depilation (except eyebrow shaping)	30 days	Prohibited [Eyebrow shaping (except for tweezing) is prohibited during the study]
Systemic retinoid (including high-dose vitamin A > 10,000 units per day)	180 days	Prohibited

6 SUBJECT TREATMENT

6.1 Investigational Products

6.1.1 Description

The investigational products are:

1. DFD-03 Lotion (0.1% tazarotene)
(60 mL bottle containing 50 mL of study product, [name] Ltd.)
2. Tazorac (tazarotene) Cream, 0.1%
(60 g tube, Allergan, Inc., USA)

The study products will be provided by [name] Ltd.

6.1.2 Labels and Packing

Bottles will be packed individually. Labels on the bottles will be in English and Spanish and include the protocol number, a unique bottle number, site number and PI name, investigational use warning, storage conditions, brief instructions for use, and sponsor name and address. In addition, there will be a place to write the subject number and subject initials. The bottle label will also have a tear-off panel that includes the protocol number and unique bottle number. The tear-off panel is to be affixed to the source document and filed in subject's chart.

6.1.3 Accountability

Documentation of receipt, study product inventory, and return shipments of the study product must be maintained at each study site. Upon receipt of the study product supplies, an inventory must be performed. It is important that site personnel count and verify that the shipment contains all the items noted in the shipment record and that they are in good condition. At study completion, all bottles of study product, used and unused, must be returned to the sponsor or designee.

In addition, an Investigational Product Dispensing Record showing dispensing to and return by clinical site staff must be maintained at the study site.

6.1.4 Dispensing

All applications of study product will be performed at the clinical site. Clinical site staff will dispense bottles of Test product or tubes of Reference cream as assigned to the subject.

At the end of the trial, all used and unused bottles and tubes must be held at the clinic for eventual destruction by the sponsor or designee.

6.1.5 Storage

Study product must be kept in a secure room temperature-controlled/monitored space at 20°-25°C (68°-77°F); excursions are permitted to 15°-30°C (59°-86°F).

6.1.6 Storage of Retention Samples

At the conclusion of the study, samples of study product will be stored at the investigational sites (or other Sponsor-approved storage facility) per FDA Guidance for Handling and Storage of Retention of BA and BE Testing Samples, which states that a sufficient number of samples for five times of release testing should be stored across the study sites.

6.2 Treatment Regimen

For all dosing days (except confinement days), subjects will come to the clinical site ± 1 hour of each dose application (e.g., around 7:00 pm and 7:00 am) for twice-daily application of Test product and (e.g. around 7:00 pm) for once-daily application of Reference product. Subjects will leave the clinical site after completion of the scheduled activities. On Day 1, subjects will come to the clinical site prior to the evening dose application (the first study treatment) and on Day 14 and Day 21 subjects will come to the clinical site before scheduled dosing allowing sufficient time for all pre-dosing assessments to be performed. The daily application time should be set based on the time of Day 1 application and should be followed for all applications through Day 22.

For each treatment arm, approximately 5 grams of Test or Reference product will be applied by the subject to the face, neck, and upper chest and will be applied by a member of the clinical staff to the shoulders and upper back (with the total area not exceeding 15% of the body surface area) over 21 consecutive days (Days 1 to 21). The study product should be applied to all affected areas [face, neck, upper chest, and/or upper back (including shoulders)] avoiding contact with the eyes, eyelids, and mouth. Subjects will be asked to refrain from applying emollients (moisturizers, creams) to the application areas at least an hour before dose application.

Note: For age group 9-11 years 11 months, approximately 4 grams of test product will be applied considering their lesser BSA.

The following steps should be taken to ensure consistent product application across time points and subjects:

1. Weigh the empty boat and record weight (e.g. 2.38g)
2. Dispense 5g of product into the boat and record total weight (e.g. 7.38g) [For age group 9-11 years 11 months, dispense 4g of test product into the boat and record total weight (e.g. 6.38g)]
3. Dose the subject
4. Put the empty boat on the scale and record the final weight (e.g. 2.41g)
5. Subtract the full boat weigh from the final weight to get the total weight of product applied ($7.38-2.41 = 4.97\text{g}$) [For age group 9-11 years 11 months, subtract the full boat weight from the final weight to get the total weight of product applied (e.g. $6.38-2.41 = 3.97\text{g}$)]

Study staff should wear gloves at all times while handling or applying the study product. If powdered gloves are worn, they should be rinsed and dried prior to handling study product.

Test Product

The Test product will be applied twice daily, 12 hours apart (± 1 hour) (morning and evening), for 21 days (42 consecutive doses). Before each dose application, subjects will take a brief warm shower to wet their skin. Approximately 5 grams of the product will be applied by the subject to the face, neck, and upper chest and will be applied by a member of the clinical staff to the shoulders and upper back, and rubbed into the skin until foamy (approximately 30 seconds for the total application area). After being left on for about 1 minute, the subject will rinse off the Test product in the shower for about 1 minute. On Day 22, the last dose application in morning will not be rinsed off in the shower; however, the subject will be permitted to towel dry after the Test product has been on for approximately one minute. Twelve hours following the last application,, the subject will rinse off in the shower for 1 minute. The subject should bare their exposed body parts when the product is rinsed off and the clinical staff should ensure that no residues are left on the body.

Note: For age group 9-11 years 11 months, approximately 4 grams of test product will be applied considering their lesser BSA.

Reference Product

The Reference product will be applied to dry skin once daily in the evening for 21 consecutive days. There should be a 24 hour interval between applications (± 1 hour). Approximately 5 grams of the product will be applied by the subject to the face, neck, and upper chest and by a

member of the clinical staff to the shoulders and upper back. The applied cream will be left on for 12 hours and showering will not be permitted until at least 12 hours after the application.

All Subjects

The times of dose applications should be recorded on the case report form (CRF).

Heavy make-up used to cover-up blemishes and sunscreen should be removed before study product application using a gentle cleanser approved by the investigator, such as Cetaphil Gentle Skin Cleanser, etc.

Subjects will be allowed to use an investigator-approved cleanser, face wash, sunscreen, and/or non-comedogenic moisturizer with SPF daily on the face. Subjects will be instructed to continue to use their investigator- approved products for the duration of the study and should avoid any changes in these consumer products.

6.3 Treatment and Protocol Compliance

Subjects will be provided an instruction sheet. Study staff should review the instruction sheet with the subjects to ensure protocol compliance.

Subjects will be instructed not to use any other topical medicated treatments or products on the face (sunscreens are allowed); and to avoid contact with eyes, eyelids, and mouth. Subjects will be allowed to use an investigator-approved cleanser, face wash, sunscreen, and/or non-comedogenic moisturizer with SPF daily on the face. Subjects will be instructed to continue to use their investigator- approved products for the duration of the study and should avoid any changes in these consumer products. Subjects will be asked to refrain from applying emollients (moisturizers, creams) to the application areas at least an hour before dose application. For subjects receiving the Reference product, they will be reminded to leave the applied cream on their skin for 12 hours and showering will not be permitted until at least 12 hours after the application. The Subject Instructions will be reviewed with each subject.

At each visit, the investigator will ask about compliance with protocol requirements. Protocol deviations will be recorded in the subject's chart and Protocol Deviation Form and included in the study report. A Protocol Deviation Form is not needed for missed visits, missed applications, out-of-window visits, or missing data. These items will be apparent from the missing data on the CRF and will be identified programmatically during data analysis for purposes of reporting. The sponsor should be consulted before discontinuing a subject due to protocol deviations unless safety is a concern.

Any subject missing dosing > 1 day (more than one dose of Reference product or two consecutive doses of Test product) from Days 7 to 14 and missing dosing between Days 12 and 14 will be removed from steady-state estimation at Day 14 but will be assessed for steady-state estimation at Day 21, provided the subject does not miss dosing between Days 19 and 21. Subjects missing dosing between Days 12 and 14, and between Days 19 and 21 will not be considered for steady-state estimation or PK and statistical analysis.

6.4 Method of Assigning Subjects to Treatment Groups

Each subject will be assigned a unique identification number upon screening. Subjects who complete the study screening assessments and meet all eligibility criteria will receive the treatment as per randomization, the order of which will be according to randomization scheme generated for each site.

The investigator shall ensure that study products are only used by subjects under investigator supervision or under supervision of sub-investigator, responsible to investigator and in accordance to the study protocol.

6.5 Blinding

Study treatment will be open-label during the study conduct. However, the plasma samples provided to the designated laboratory for determination of tazarotene and tazarotenic acid will be coded to ensure that the identity of the treatments is not known when the plasma samples are analyzed.

6.6 Prior and Concomitant Therapy and Procedures

Chronic medications being used at the time of the Screening and Baseline Visit, except for those specified as prohibited, may be continued at the discretion of the investigator. History of medications, therapies, and procedures is collected from the prior 6-month period for determination of eligibility. Only medications, therapies and procedures in use during the study should be entered on the CRF.

New medications used after baseline required for another medical condition, that in the opinion of the investigator will have no material impact on the study, are permitted. The addition of such a new medication during the study will be documented as a concomitant medication and the associated medical need must be recorded as an AE, if applicable.

All medications (topical, oral, prescription, over-the-counter, and herbal medications) and medical therapies or procedures that are used during the study for other diseases/conditions must be recorded on the CRF.

Subjects will only be allowed to use an investigator-approved gentle cleanser, facial wash, sunscreen, and/or non-comedogenic moisturizer with SPF. Use of non-medicated make-up is allowed.

Subjects should be instructed to refrain from making any significant change in the use of consumer products during the study. Any changes will be captured in the source documents and CRF. The name and the date that the new product was started will be recorded.

See [Table 4](#) for a list of medications and procedures that are prohibited during the study.

6.7 Study Restrictions

Only the assigned study product and investigator-approved sunscreen/moisturizer with SPF, gentle cleanser, face wash, and non-medicated make-up should be applied to the face during the study.

Subjects must be willing to comply with sun avoidance measures for the face (and chest and/or back, including shoulders if applicable) including use of investigator-approved sunscreen and/or hats, have limited sun exposure time, and have no tanning bed use.

Subjects should abstain from alcohol for 72 hrs prior to first dosing and during study duration. Subjects who are smokers should be reminded to smoke no more than 10 cigarettes per day (or the equivalent for other nicotine containing products) during non-confinement days (except Day 13 and Day 20). They should also be instructed to abstain from smoking or using any products containing nicotine (including electronic cigarettes) 1 day prior to confinement days (Day 13 and Day 20) and during confinement.

7 STUDY PROCEDURES AND EVALUATIONS

7.1 Informed Consent Process

Informed consent must be obtained before a subject can participate in the study, prior to performing any study related procedures and before withdrawal of any therapies prohibited during the study. The investigator must discuss the study fully with the subject (and legal guardian, as applicable). Subjects must demonstrate their willingness to participate in the study and comply with the study procedures by giving written informed consent or written assent, as applicable. The consent form and “Information and assent” form must be signed and dated by the subject or legal guardian, as applicable. A copy of the consent form (and “Information and assent” form, as applicable) must be given to the subject and/or legal guardian, and the date of the consent process and who conducted the consent process must be documented in the source documents.

7.2 Screening

An initial Screening visit should be scheduled to occur approximately 19 days (Day -21 to Day -1) prior to the Baseline visit (Day 1). The subject number, date of visit, date of consent, reason for screen failure, and study status (screen failure) will be captured in the CRF for every screen failure subject. Medical history and acne history should be collected for the prior 1-year period and concomitant medications, therapies, and procedures collected for the prior 6-month period. Only ongoing medical conditions and ongoing concomitant medications should be entered on the CRF. Acne history will be collected and recorded in the CRF.

A history of tobacco, alcohol and drug use should be reviewed and collected. Presence of alcoholism (i.e. alcohol in excess of 14 glasses/units per week, with one unit = 150 ml of wine or 360 ml of beer or 45 ml of 45% alcohol) and a history of drug abuse within 2 years prior to first dose will be determined and recorded.

A screen failure is a subject who received information about the study, including signing an informed consent and possibly performing some study-related procedures, but was not randomized and/or did not use study product.

7.3 Demographic and Baseline Characteristics

Demographic variables include age (computed from date of birth and Day 1 date), race, ethnicity, and sex. Baseline characteristics include IGA and lesion counts of the face.

7.4 Acne Evaluation

7.4.1 Lesion Counts of the Face

Non-inflammatory lesions (closed comedones and open comedones), inflammatory lesions (papules and pustules), and nodulocystic lesions (nodules and cysts) on the face (above the mandibular line), including the nose, will be counted and recorded separately at Screening/Baseline to determine study eligibility. Non-inflammatory lesions of acne are the open (blackheads) or closed (whiteheads) comedones. Closed comedones may be more difficult to detect visually and may require stretching of the skin to aid in visualization. Inflammatory lesions are divided into papules, pustules, and nodules/nodulocystic lesions, depending on the severity and location of the inflammation within the dermis. Nodulocystic lesions will be counted separately from inflammatory lesions of papules and pustules. The papules and pustules

have surrounding halos of erythema allowing for their characterization as inflammatory. Nodules are typically erythematous and often tender and/or painful. Additionally, they are deep-seated in the skin (i.e., centered in the dermis or subcutis). Nodules have been defined as being greater than 5 mm in diameter. The borders of these lesions may be difficult to determine because of the associated erythema/inflammation. The investigator/evaluator should use standard, good lighting to visualize lesions and a systematic counting procedure to ensure accurate counts. The investigator will perform lesion count at Screening and the baseline visit (Day1) and at PK sampling days at Day 15 (prior to evening dose application), Day 21 (post last evening dose application for Reference treatment) and Day 22 (post last morning dose application for Test treatment).

Disease severity will be assessed by IGA, inflammatory and non-inflammatory lesion count (% change from baseline for lesion count) at Day 15 and Day 21/Day22.

7.4.2 Investigator’s Global Assessment (IGA) of the Face

The IGA will be performed by the investigator, with best attempts made to assign the same evaluator for a subject throughout the study to obtain consistency in grading scores. The IGA will be performed at Screening and the baseline visit (Day1) and at PK sampling days at Day 15 (prior to evening dose application), Day 21 (post last evening dose application for Reference treatment) and Day 22 (post last morning dose application for Test treatment).

The IGA scale to be used in the study is a measure of static evaluation of qualitative overall acne severity. IGA is an ordinal scale with five severity grades (reported only in integers, e.g., 0 to 4). Each grade is defined by a distinct and clinically relevant morphologic description to minimize inter-observer variability (Table 5). The grades on the scale have been sufficiently defined to appropriately and unambiguously represent each severity grade on the scale. The investigator will perform IGA scoring at Screening and the baseline visit (Day 1). To be enrolled, subjects had to have an IGA score of 3 at Baseline (Day 1). Disease severity will be assessed by the Investigator’s Global Assessment (IGA) score at baseline and PK sampling days.

Table 5: IGA Scale for Facial Acne Vulgaris*

Grade	Description
0	Clear skin with no inflammatory or non-inflammatory lesions
1	Almost clear; rare non-inflammatory lesions with no more than rare papules
2	Mild severity; some non-inflammatory lesions with no more than a few inflammatory lesions (papules/pustules only, no nodular lesions)
3	Moderate severity; up to many non-inflammatory lesions and may have some inflammatory lesions, but no more than one small nodular lesion
4	Severe; up to many non-inflammatory and inflammatory lesions, but no more than a few nodular lesions

* Areas other than the face and nose are not included in assessment

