Reference Product: Tazorac (tazarotene) Cream, 0.1%, Manufacturer: Allergan, Inc., USA

The Reference product will be applied to dry skin once daily in evening for 21 consecutive days. There should be a 24 hour interval between applications (\pm 1 hour). Approximately 5 grams of the product will be applied by the subject to the face, neck, and upper chest and will be applied by a member of the clinical staff to the shoulders and upper back. The applied cream will be left on for 12 hours and showering will not be permitted until at least 12 hours after the application.

Duration of Treatment and Study:

Study products will be applied daily for 21 days (twice daily for the Test product and once daily for the Reference product). The total study duration including the screening period will be approximately 6 weeks.

Housing: Subjects will be confined to clinic as per the following schedule:

Day 1: From prior to the first (evening) dose application of Test or Reference treatment at the Baseline visit, allowing sufficient time for all pre-dosing assessments to be performed, until after the evening dose application for assessing baseline disease severity, blood sampling, and dosing

Days 14-15: From prior to the Day 14 evening dose application of Test or Reference treatment, allowing sufficient time for all pre-dosing assessments to be performed, until after collection of the 24-hour PK sample, disease severity assessment, and the Day 15 evening dose application. For pediatric population in Part B of the study, the PK samples will be collected as per [Table 3](#).

Days 21-22: From prior to the evening dose application of Test or Reference treatment, allowing sufficient time for all pre-dosing assessments to be performed, until after collection of the 24-hour PK sample on Day 22 and following disease severity assessment after the last dose application (evening dose application on Day 21 for Reference treatment or morning dose application on Day 22 for Test treatment). For pediatric population in Part B of the study, the PK samples will be collected as per [Table 3](#).

Wash-out: None; parallel design

Bioanalysis: Tazarotene and tazarotenic acid plasma concentrations will be measured by a validated bioanalytical LC-MS/MS method.

Criteria for Evaluation:

Pharmacokinetics:

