Lesion count ⁵	X	X						X		X	X ⁵
Serology (HIV Ag/Ab Combo, Hepatitis B (HBsAg (B)) and Hepatitis C (anti-HCV (C), Serum Pregnancy Test.	X										
Urine pregnancy test ⁶		X		X			X			X	
Drug screen (urine)	X	X		X			X			X	
Alcohol breath test	X	X		X		X	X	X (Day 19)	X	X	
Physical examination	X	X								X	
Height	X										
Weight	X	X									
Vital signs ⁷	X	X	X	X	X	X	X ⁷	X	X	X ⁷	X ⁷
12-Lead ECG	X	X								X	
Clinical safety blood sample	X	X								X	

Table 1 Continued: Overall Study Procedure and Schedule of Assessments

Procedure or Assessment	Screening Visit	Treatment Application (21 Days)									
	(Day -21 to Day -1)	Baseline Visit (Day 1)	2to 6	7	8 to 11	12 to 13	14	15 to 19	20	21	22
PK blood samples ⁸		X				X ⁸	X	X ⁸	X	X	X
Disease Severity Assessment ⁹		X						X		X	X
Concomitant medications	X	X	X	X	X	X	X	X	X	X	X
Assess for local cutaneous adverse reactions ¹⁰		X	X	X	X	X	X	X	X	X	X
Adverse events ¹¹	X	X	X	X	X	X	X	X	X	X	X
End of study											X

1. Update medical history/prior medication
2. Test product: Twice daily morning and evening (12 hours apart, \pm 1 hour), Reference product: Once daily in evening (24 hours apart, \pm 1 hour).
3. All subjects will be confined at the clinical site on PK sample collection Day 14 and Day 21 (after evening dose application). On Day 15, the subjects will leave clinic after completion of evening dose application for Test Product and Reference product. On Day 22 subjects will leave clinic after collection of 24-hr blood sample. Test product last dose will be applied on Day 22 morning.
4. Evaluation by IGA score at Screening, prior to the evening dose application for Test and Reference treatment on Day 1, before evening dose application on Day 15 for Test and Reference treatments, and before evening dose application on Day 21 for Reference and before morning dose application on Day 22 for Test treatment.
5. Lesion count will be performed before evening dose application on Day 1 and Day 15 for Test, and Reference treatments and after evening dose application on Day 21 for Reference and morning dose application on Day 22 for Test treatment.
6. For females of childbearing potential on Day 7, Day 14 and Day 21.

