2. On Day 21, update concomitant medications.
3. On Day 21 prior to evening dose application in evening for Test and Reference treatments, perform urine pregnancy test for female subjects, urine drug screen and alcohol breath test. Any subject with a positive alcohol breath test and/or positive drug screen should be discontinued.
4. On Day 21, perform 12-lead ECG pre-dose.
5. Prior to dosing on evening of Day 21 for Reference treatment and morning treatment of Day 22 for Test treatment, assess severity of acne by IGA scoring and measurement of lesion count. IGA scoring will be done prior to lesion count.
6. Prior to each dose application, visually inspect the skin and record erythema and scaling grades.
7. Apply assigned study product for the Day 21 evening dose application for Test and Reference treatments. For subjects assigned to Test treatment, the morning dose application will be performed the morning of Day 22 and this last dose application will not be rinsed off in the shower.
8. After each dose application, perform local cutaneous safety evaluation for dryness, non-lesional erythema, and peeling within 1 hour of dosing. The investigator or designated trained site staff should also ask the subject if any burning, stinging, or itching has occurred on the face since the last application. These evaluations should be recorded separately for the face and, if applicable, chest/back (including shoulders).
9. On Day 21, collect sitting vital signs (blood pressure and pulse) pre-evening dose and at 1 and 8 hours after evening dose application for Test and Reference treatments. (Note that the 8-hour post dose vital sign will occur on the morning of Day 22).
10. On Days 21 to 22, PK blood sample collection will occur at the following times:

In Part A (adults, age 17 years or older), blood samples will be collected prior (pre-dose) to the Day 21 evening dose application for Test and Reference treatments and at 1, 2, 4, 6, 8, 12, 14, 16, 18, and 24 hours post dose application.

In Part B for Test treatment (subjects age 9 years to 16 years 11 months) and Reference treatment (subjects 12 years to 16 years 11 months), a maximum of 4 blood samples will be collected as per the sparse sample design ([Table 3](#)).
11. On Day 21, collect blood sample for safety laboratory evaluations (chemistry, hematology, and urinalysis).
12. Collect AE data.
13. Complete CRF.

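### The protocol contradicts itself on whether the final IGA and lesion counts are done before or after the last dose

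*Combined protocol and SAP*

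**What the plan says.** Five places in the protocol time the final disease severity assessment relative to the last dose.

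- Table 1 footnote 4, for IGA: "before evening dose application on Day 21 for Reference and before morning dose application on Day 22 for Test treatment".
- Table 1 footnote 5, for lesion counts: "after evening dose application on Day 21 for Reference and morning dose application on Day 22 for Test treatment".
- Section 7.4.1, for lesion counts: "Day 21 (post last evening dose application for Reference treatment) and Day 22 (post last morning dose application for Test treatment". Section 7.4.2 gives the same post-dose timing for IGA: "Day 21 (post last evening dose application for Reference treatment", and likewise on Day 22 for Test.
- Section 7.10.4 item 5: "Prior to dosing on evening of Day 21 for Reference treatment and morning treatment of Day 22 for Test treatment, assess severity of acne". The item covers both measures, since the instruction is to "assess severity of acne by IGA scoring and measurement of lesion count".
- Synopsis, Housing, Days 21-22: confinement runs until after the 24-hour PK sample and "following disease severity assessment after the last dose application".

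The earlier visits are consistent. Footnote 4 sets the baseline IGA "prior to the evening dose application for Test and Reference treatment on Day 1", and footnote 5 and Section 7.10.2 item 3 agree for lesion counts. Day 15 is before the evening dose in both footnotes and in Sections 7.4.1, 7.4.2 and 7.10.3 item 6.

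These readings serve secondary objective (a) in Section 3. Section 11.4 compares baseline with the sampling days by a paired t-test or another suitable test, presented by treatment. Lesion counts are expressed as percent change from baseline.

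**The concern.** For each measure, a site cannot follow one instruction without breaking another. The two sites could do different things, each in line with some part of the protocol, and neither would see a deviation.

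A before-and-after comparison assumes that the two readings are taken under like conditions. If the final reading follows the dose, it is taken with product recently applied to the face, while the baseline and Day 15 readings are not. Residue, or an acute reaction to the application, could then change the score in addition to any change in acne. Section 7.4.1 says that papules and pustules are recognised partly by the redness around them, and Section 7.6 expects erythema, peeling and dryness to be looked for after each dose, so a route for such an effect exists in the protocol's own terms.

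**Working it through.** No figure in the plan bears on this point, so the check is a comparison of the texts.

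| Place | Final IGA | Final lesion count |
|---|---|---|
| Table 1 footnote 4 | before dose | not covered |
| Table 1 footnote 5 | not covered | after dose |
| Section 7.4.1 | not covered | after dose |
| Section 7.4.2 | after dose | not covered |
| Section 7.10.4 item 5 | before dose | before dose |
| Synopsis, Housing | after dose (general wording) | after dose (general wording) |

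Among the statements specific to a measure, IGA has two before and one after, and the lesion count has one before and two after. The Housing text adds a general post-dose statement. Footnotes 4 and 5 concern different measures, so they do not contradict each other. The text as a whole nevertheless supports three schedules: both measures before the dose (Section 7.10.4), both after (Sections 7.4.1 and 7.4.2, Housing), and IGA before with lesion count after (Table 1).

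**Which timing matches the earlier visits.** Test is dosed every 12 hours and Reference every 24 hours, each with a window of 1 hour either way.

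- Day 15 before the evening dose: Test was last dosed on Day 15 morning, 12 hours earlier; Reference on Day 14 evening, 24 hours earlier.
- Final reading before the last dose: Test (Day 22 morning) was last dosed on Day 21 evening, 12 hours earlier; Reference (Day 21 evening) on Day 20 evening, 24 hours earlier.
- Final reading after the last dose: the interval is unspecified, because no post-dose window is given.

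Pre-dose timing therefore reproduces the Day 15 conditions in both arms. It also keeps the final Test reading after a rinsed application, because only the Day 22 morning dose is left unrinsed.

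**Whether a post-dose effect could differ by arm.** On Day 22 the Test product stays on for 12 hours, with towel drying allowed after about a minute. The Reference cream is applied to dry skin and left on for 12 hours. These are different skin conditions, so an effect, if there is one, need not be equal.

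**Whether it could be recovered at analysis.** Section 6.2 requires dose times on the CRF. No instruction was found to record the time of the IGA or lesion count.

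**Extent.** There are two post-baseline severity assessments (Day 15 and Day 21/22), and one of them is affected, for those subjects whose site follows the post-dose text.

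**The case against.** The conflict in wording has no good answer, but its consequence can be disputed, and several of the counter-arguments stand.

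- The endpoint is secondary and open-label, the study is not powered (Section 11.1), and the severity analysis is within treatment. Day 15 is consistently pre-dose. All of this stands and limits the importance.
- The applied amount is spread over the face, neck, upper chest, shoulders and upper back, up to 15% of body surface, while IGA and lesion counts concern the face only. Rubbing until foamy is described for Test alone. This stands: how much product lies on the assessed skin is not stated.
- Because no post-dose interval is given, a post-dose reading need not be an immediate one. This stands, so an acute effect is possible and not shown.
- Non-lesional erythema is graded separately (Table 6), and the IGA grades in Table 5 do not mention erythema. After three weeks of treatment, irritation may also be present before a dose. So pre-dose timing makes the visits comparable but does not remove irritation from the score.
- For lesion counts, most statements are post-dose. This is true, and the choice of pre-dose timing rests on agreement with Day 1 and Day 15 and not on a count of statements.

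A reader might infer that the final severity results are biased, or that the protocol deliberately chose a post-dose reading. The documents support neither. They do not show what the sites did, and they give no size or direction for an effect: residue could hide lesions, while redness could add apparent ones.

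**Conclusion.** The point holds as an internal inconsistency. For both IGA and lesion count, the current text gives opposite instructions about the final assessment relative to the last dose. A post-dose reading would make the comparison of baseline with Day 21/22 unlike in timing at that visit only.

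The consequence is conditional. It arises only if a site reads post-dose, and only if residue or an acute reaction on the face alters the score. No figure in the documents allows that effect to be sized, so none is offered. A numerical shift in percent change would rest on an invented number of miscounted lesions. The primary PK comparison and the Day 15 severity comparison are not affected. The correction is still worth making because it is cheap and because, without recorded times, the mixture may not be separable later.

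**What to change.** Reconcile Table 1 footnote 5, Sections 7.4.1 and 7.4.2 and the synopsis Housing text with footnote 4 and Section 7.10.4 item 5. Both final IGA and final lesion count should be done before the last dose (Day 21 evening for Reference, Day 22 morning for Test), as on Day 1 and Day 15. Changing only the two subsections and the footnote would leave the Housing text in conflict.

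Add the clock time of each IGA and lesion count to the CRF, next to the dose time already recorded there.

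Part A precedes Part B, and Section 7.5 says its PK assessment has been conducted. Where source records show that a Part A final assessment was done post-dose, identify it in the analysis. The documents do not say that these times were recorded, so this may not be possible for every subject. The separate statistical analysis plan, due before database lock, can state how such readings are handled.

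The cost is wording in four places and one CRF field, with no added procedure and no change to dosing.
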